11 control tool in use in the population, houses in the same location without the intervention is ideal.

12

13 **Intervention description {11a}**

14 **Intervention group**

15 The intervention is hardware insecticide treated netting that is used to cover the eaves (gaps
16 between the wall and roof) of houses and to screen windows. The insecticides coated in the ITENS
17 and ITWS are deltamethrin at 3g AI/kg, which corresponds to 144 mg/m² and PBO synergist at
18 10g/kg which corresponds to 480 mg/m², as used in the so-called dual-AI LLIN or “resistance
19 breaking” nets (6). The nets were manufactured by Moon Netting FZCO, United Arab Emirates.
20 The combinations of deltamethrin and PBO synergist has been shown to be efficacious against
21 pyrethroid resistant Anopheline mosquitoes and malaria (12). These nets are supplied on a roll and

1 attached to the wood around the roof, frame of the windows and on wood between walls using
2 staple guns and hammer. The nets will be used to cover all obvious mosquito entry points
3 including open eaves, windows and holes in house walls of between 10–25 cm diameter.

4

5 **Criteria for discontinuing or modifying allocated interventions {11b}**

6 Participants are free to withdraw from the study and they will be given the option to either keep
7 the intervention or uninstall the nets from the eaves and windows. If perceived unacceptable
8 adverse effects related to the intervention are reported by the participants, the intervention shall be
9 removed upon the request of the participants by the study team, as this is also discussed in the
10 Informed Consent form (Annex 1).

11

12 **Strategies to improve adherence to interventions {11c}**

13 ITENS and ITWS are hardwearing insecticide treated netting, thus minimal risk of non-adherence.
14 Houses allocated to the negative arm will have ITENS and IWS installed at the end of the trial.

15

16 **Relevant concomitant care permitted or prohibited during the trial {11d}**

17 At each survey, clinical officers/nurses/clinicians will withdraw blood samples from all
18 participants with an axillary temperature of 37.5 degrees or over for malaria parasites using a SD
19 Bioline Malaria Ag Pf/Pan rapid diagnostic test (RDT) for point of care as per Tanzania Ministry
20 of Health guidelines, and to establish clinical malaria cases. Any participant (s) that tests positive

1 using mRDT will be treated using free Artemether Lumefantrine (ALu). This drug is approved by

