2 the national guideline for treatment of uncomplicated malaria (13).

3

4 **Provisions for post-trial care {30}**

5 ITENs & ITWS will be installed in houses randomly selected in the negative control arm at the
6 end of the trial to ensure that all groups have access to the intervention.

7

8 **Outcomes {12}**

9 **Primary outcome**

10 Prevalence of malaria measured by qPCR shortly after long rainy season (June/July, year 2022) in
11 households with ITENs and ITWS installed in comparison to those without.

12 **Secondary outcomes**

13 - Prevalence of malaria measured by qPCR shortly after the short rainy season (January/
14 February 2022) in households with ITENs and ITWS installed in comparison to those without.

15 - Prevalence of clinical malaria cases (defined by axillary temperature of 37.5 degrees or above
16 and positive mRDT) shortly after the short rainy season (January/February 2022) and long
17 rainy season (June/July 2022) in households with ITENs and ITWS installed in comparison to
18 those without.

19 - Density of malaria vectors and nuisance mosquitoes present in houses with ITENs and ITWS
20 installed in comparison to the houses without after the short (January/February 2022) and long
21 (June/July 2022) rainy season measured by CDC light trap.

- 1 - The amount of fabric and time cost of installing ITENs and ITWS per house.
- 2 - The percentage of adverse effects among technicians and houses with ITENs and ITWS after
3 one month of installation.
- 4 - The physical presence and numbers of holes visually observed in ITENs and ITWs after 6
5 months and 12 months of installation.
- 6 - The percentage knockdown and mortality at 24 hours of ITENs and ITWs after 12 months of
7 installation.
- 8 - The percentage chemical content of ITENs and ITWs after 12 months of installation.
- 9 - The percentage acceptance of ITENs and ITWS in the community using the structured
10 questionnaire.
- 11 - The behaviour, practice and use of ITENs and ITWS in the community from FGDs.

12

13

14

15

16

17

18

19

20

21

1 **Participant timeline {13}**

	STUDY PERIOD							
	Enrolment	Allocation	Post allocation					Closeout
TIMEPOINT	May	June, 2021	Aug 2021	Dec, 2021	Jan, 2022	June, 2022	July, 2022	Sept, 22
Eligibility screen/ baseline data	X							
Informed consent / Allocation	X							
Installation in the intervention arm		X						
Installation in the control arm								X
ASSESSMENTS								
Perceived adverse effect			X					

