9 quantitative polymerase chain reaction (qPCR) analysis. Point of care diagnosis for febrile
10 individuals will be SD Bioline Malaria Ag Pf/Pan rapid diagnostic test (RDT) as per Tanzanian
11 guidelines (13).

12 Used RDT kits will be stored in a locked shipping container at IHI until the data is completed and
13 locked, then the samples will be destroyed on-site in the Clinical Trials facility Incinerator.

14

15 **Statistical methods**

16 **Statistical methods for primary and secondary outcomes {20a}**

17 The primary endpoint which is detection of malaria parasitemia through qPCR after the long rainy
18 season (June/July 2022) will be analysed using mixed effects binary logistic regression, with a
19 random effect for household to account for clustering. Analysis of secondary endpoints malaria
20 parasitemia will be tested using qPCR after the short rainy season (January/February 2022) as well

1 as clinical malaria cases and malaria prevalence shortly after the short rainy season and long rainy
2 will also be analysed following the same approach.

3 Negative binomial mixed effect model will be performed for mosquito density data, with random
4 effect for household.

5 The baseline characteristics collected during the survey, including age, sex, education, number of
6 participants, household size, occupation, sleeping spaces, nets per house, nature of houses (wall,
7 roof, and floor), community acceptance of LLINs (use rate and any side effects) and
8 socioeconomic quintiles will be presented by arm.

9 Principal component analysis (PCA) will be carried out to determine a combination of variables
10 for socioeconomic status to explain the overall observed variation and reduce the complexity of
11 the data, by calculating a weighted score for the socioeconomic status of each household of the
12 population and divided into five quintiles: lowest, low, middle, high and highest.

13 Proportion of the outcomes (attrition, fabric integrity and community acceptance) will be presented
14 in percentages.

15 Recorded information during the FGD will be transcribed and grouped into different themes based
16 on inductive thematic analysis of interview summaries. Reports will be illustrated with verbatim
17 quotes of themes and sub-themes identified.

18

19 **Interim analyses {21b}**

20 No interim analyses will be carried out.

21

1 **Methods for additional analyses (e.g. subgroup analyses) {20b}**

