2 An analysis of the intervention effect within subgroups defined by age (under 5s, aged 5-15, and
3 aged 16 or over), socioeconomic status, gender, among others will be carried out on malaria
4 prevalence at both surveys using the same methods as for the primary endpoint.

5

6 **Methods in analysis to handle protocol non-adherence and any statistical methods to handle**
7 **missing data {20c}**

8 Minimal protocol non-adherence is expected because of the nature of the intervention, however
9 we will carry out an intention to treat in which households are analysed according to allocation
10 regardless of whether the intervention was adhered to. A secondary per protocol analysis which
11 excludes houses that removed the intervention will be carried out. At an individual level,
12 participants who report being away from home for more than a week during the fortnight preceding
13 testing will be excluded from the primary analysis but included in a secondary analysis. We expect
14 there to be minimal missing data on the primary endpoint, in which case complete case analysis
15 will be used. If there is more missing data than expected, a secondary analysis in which multiple
16 imputation is applied under the assumption of missing at random will be carried out.

17

18 **Plans to give access to the full protocol, participant level-data and statistical code {31c}**

19 Full protocol, statistical analysis plan, anonymized level-data and statistical code will be made
20 available on reasonable request.

21

1 **Oversight and monitoring**

2 **Composition of the coordinating centre and trial steering committee {5d}**

3 The Ifakara Health Institute is the trial sponsor and coordinating centre. Study investigators meet
4 weekly to review trial progress. A trial steering committee consisting of study investigators and
5 independent experts will meet after every study survey.

6

7 **Composition of the data monitoring committee, its role and reporting structure {21a}**

8 Although we don't anticipate any safety issues in this trial since the intervention is similar to LLINs
9 which are used extensively in malaria endemic regions a data monitoring committee has been
10 appointed. The committee is composed of a clinician, an entomologist and a statistician, is
11 independent of the trial sponsor and funder, and has no competing interests. The committee will
12 meet after the data from each survey have been collected. The committee will consider safety data

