13 and data on trial endpoints and make recommendations on whether the trial should continue.

14

15 **Adverse event reporting and harms {22}**

16 The assessment of the risk to humans by the World Health Organization (WHO) (17) is that no
17 unacceptable exposures were found in maintenance and use of insecticides incorporated or coated
18 with deltamethrin and PBO synergist, and that washing or sleeping under them does not pose undue
19 risk to adults. Moreover, there is reduced contact with ITENs and ITWs. Nevertheless, participants
20 will be advised on possibilities of adverse effects. In case of serious adverse effect related to the

1 use of the study items, although not expected, affected participants will be provided with free
2 medical care.

3 An assessment of adverse effects will be made using a questionnaire given in Appendix 1, and will
4 be administered to carpenters and technicians as well as 50 randomly selected households in the
5 village at four weeks post-installation of ITENs and ITWS. The households will be selected by the
6 statistician using a simple random selection procedure blocked at sub-village level. The Principal
7 Investigator shall inform the Bagamoyo District Medical Officer and the IHI ethical review board
8 about possible reporting of adverse effects of use of ITENs and ITWS by the participants.

9

10 **Frequency and plans for auditing trial conduct {23}**

11 No trial audit is anticipated.

12

13 **Plans for communicating important protocol amendments to relevant parties (e.g. trial** 14 **participants, ethical committees) {25}**

15 Any protocol amendments and/or deviations will be fully justified and documented and agreed
16 upon by the sponsor study investigators, and village representatives. Application for such protocol
17 amendment will be written to the ethics committee and for clearance. If approval is attained from
18 the ethics committee, the changes to the protocol will be communicated to the participants via
19 village leaders and during study follow up.

20

21 **Dissemination plans {31a}**

1 Data will be disseminated by report to the sponsor, followed by peer-reviewed publication targeted
2 towards consumers, scientists and policy-makers. We will publish the results and data sets in open-
3 access, indexed, peer-reviewed journals, making the findings and the anonymized data publicly
4 available to all stakeholders. Data obtained from the study will be presented at international

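### Does the data monitoring committee's look at endpoint data after each survey contradict the statement that there are no interim analyses?

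*Protocol*

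**What the plan says.** Interim analyses {21b}, within the Statistical methods part of the protocol, states: "No interim analyses will be carried out".

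The section on the data monitoring committee {21a}, within Oversight and monitoring, describes an independent clinician, entomologist and statistician who will "meet after the data from each survey have been collected. The committee will consider safety data" "and data on trial endpoints and make recommendations on whether the trial should continue". The section on the steering committee {5d} adds that a group of investigators and "independent experts will meet after every study survey".

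Trial design {8} gives two surveys, January/February and June/July 2022. The primary outcome in Outcomes {12} belongs to the second alone: "Prevalence of malaria measured by qPCR shortly after long rainy season (June/July, year 2022) in" treated against untreated households. At the first survey, qPCR prevalence, clinical malaria and mosquito density are secondary outcomes. Statistical methods {20a} says of the secondary malaria outcomes that they "will also be analysed following the same approach" as the primary one.

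On the control arm, {11c} says: "Houses allocated to the negative arm will have ITENS and IWS installed at the end of the trial". The section on post-trial care {30} says much the same, and the participant timeline {13} puts that installation in September 2022.

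**The concern.** Read side by side, {21b} excludes interim analyses without qualification, while {21a} has a committee review accumulating endpoint data and advise on continuing. Only the meeting after the first survey can bear on the primary endpoint, because by the second meeting those data are in. At the first meeting the endpoint data are all secondary, and the qPCR and clinical outcomes have the same model as the primary analysis, so they could readily be turned into an efficacy or futility comparison. {21a} does not confine the recommendation to safety and does not say whether endpoint data are shown by arm.

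If the committee advised stopping on those data and the advice were accepted, the June/July 2022 survey would not take place and the primary outcome would never be measured. If the control houses were then fitted with nets at once, the untreated comparison would be gone.

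**Working it through.** **1. Do the passages exclude each other?**

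| | {21b} | {21a} |
|---|---|---|
| Part of the protocol | Statistical methods | Oversight and monitoring |
| Activity | analysis | committee considers data |
| Trigger | none planned | survey data collected |
| Test, threshold or comparison by arm | none | none mentioned |
| Result | – | recommendation only |

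They conflict only if considering endpoint data is itself an interim analysis. If {21b} means no planned interim test of efficacy or futility, both hold. The sentence in {20a} about a common approach names the model for the secondary outcomes. It does not say that the model is fitted, or shown to the committee, after the first survey.

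**2. Is the sample size that of a single-look trial?** Inputs from Sample size {14}: 225 houses per arm, m = 4.5 residents, p0 = 0.20, p1 = 0.14, between-house coefficient of variation k = 0.5, power 90%. The protocol states no alpha, so two-sided 0.05 is assumed.

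Hayes–Bennett formula for unmatched clusters: c = 1 + (z_α/2 + z_β)² × V / (p0 − p1)², with V = p0(1−p0)/m + p1(1−p1)/m + k²(p0² + p1²).

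- V = 0.16/4.5 + 0.1204/4.5 + 0.25 × (0.04 + 0.0196) = 0.03556 + 0.02676 + 0.01490 = 0.07721
- c = 1 + (1.960 + 1.282)² × 0.07721 / 0.0036 = 226.4 (225.4 without the added 1)
- Power with 225 per arm: 0.898 (0.900 without the added 1)
- Design-effect version: ICC = k²p0/(1−p0) = 0.0625; design effect 1 + 3.5 × 0.0625 = 1.219; about 223 houses per arm, power 0.903

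The stated figure reproduces for one final analysis, which agrees with {21b}.

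**3. Type I error.** Let Z2 be the June/July test statistic, the only one on which primary success is declared. For any rule applied after the first survey, P(trial continues and |Z2| > 1.96) ≤ P(|Z2| > 1.96) = 0.05. An earlier look can only remove chances to reject.

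Inflation would need success to be declarable at either survey, each at 0.05 without adjustment: 1 − 0.95² = 0.0975 if the surveys were independent, 0.091 at correlation 0.5 and 0.070 at 0.9. The protocol contains no such rule, so these figures do not apply.

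**4. Power.** P(continue and reject) ≥ P(reject) − P(stop). Any loss is at most the probability of an endpoint-driven stop. The protocol gives nothing from which to compute that probability, and it is zero if no such rule is operated.

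**5. Would the loss be irreparable?** The timeline puts control-arm installation in September 2022, after the primary survey. {11c} and {30} tie it to the end of the trial, but nothing says that an early stop would bring it forward. Nor does anything say that a stop would remove nets already fixed to intervention houses, from which the 12-month bioefficacy and chemical content are measured.

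**The case for a change.** The best case for a change has four parts. {21b} carries no qualifier such as formal. {21a} lists endpoint data separately from safety data. The only scheduled adverse-effect assessment is the questionnaire four weeks after installation (August 2021 in the timeline), so the main new material at the first meeting would be endpoint data. Finally, a charter could not by itself make two protocol sentences agree, and one added sentence would cost almost nothing.

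Much of this stands. The wording is loose, a pure safety reading is not spelled out, and a clarifying phrase would do no harm. It does not establish a defect in the design, for three reasons.

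- What is really asked for is a statement of what the committee sees and on what grounds it may advise stopping. A charter or SAP normally carries that; {31c} mentions a SAP, which is not at hand.
- The obvious remedy is to confine the first recommendation to safety, including any excess of malaria in the intervention arm. That still requires a look at malaria by arm, so on the strict reading {21b} would remain contradicted.
- Barring efficacy or futility advice would narrow an independent committee's remit, including its freedom to respond to a very large benefit withheld from controls. That is a trade-off for the trial team, not a correction.

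**Conclusion.** The concern does not call for a change. The mismatch is one of wording: {21b} can be read as ruling out a formal interim test, and {21a} as routine monitoring that ends in advice. A steering committee that includes independent experts also meets after each survey.

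Followed as written, the June/July 2022 primary analysis is sound. Its type I error is not inflated. If the committee does not act on first-survey endpoint data, power and the estimate are those of a single-look trial, with power of about 90% as stated. The remaining risk is a stop advised and accepted on January/February data. Its probability cannot be derived from the protocol and none is claimed.

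This rests on two assumptions: that efficacy is judged only on the June/July 2022 endpoint, as Outcomes {12} specifies, and that the test is two-sided at 0.05, which the protocol does not state. If some document let success be declared on the first survey as well, the conclusion would have to be revisited.
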